1.0 PROTOCOL SUMMARY AND SCHEMA

Triple negative breast cancer patients with metastatic or unresectable, locally advanced disease who require radiation therapy to a measurable tumor site are eligible. Prior to treatment, all patients will receive a biopsy of the tumor to be irradiated. Utilizing the Memorial Sloan Kettering Homologous Recombination Repair (MSK-HRR) Assay, patients will be identified as either HR-deficient or HR-proficient. Knowledge of the HR repair status prior to treatment is not necessary, since all patients in the study will receive the same treatment, regardless of the knowledge of the tumor- concurrent cisplatin and radiation (RT) to the tumor.

The primary purpose of the trial is to assess whether or not HR repair status is a sensitive biomarker of response, as measured by complete response (CR) rate in patients receiving cisplatin and radiation. Cisplatin will be given once a week(+ 3 days) for 1-2 weeks, followed by concurrent delivery with RT to the tumor. Following the completion of RT, pending no toxicities, but prior to the week 12 post RT evaluable timepoint, patients will continue to receive cisplatin or until POD, based on MD discretion.

Secondary objectives are to assess time to progression and overall response rate (CR+PR+SD) by HRR status. Exploratory objectives are to assess association between tumor infiltrating lymphocyte (TIL) and treatment response and to compare the effectiveness of RECIST 1.1 criteria with PET Response Criteria in metabolically active tumors.

At baseline, all patients will receive PET-CT. An MR will be obtained in addition only if the study radiologist determines that tumor is insufficiently evaluable with PET-CT. At 12 +2 weeks after completion of RT, patients will undergo the same imaging modality used at baseline assessment (PET-CT or MR) in order to assess treatment response. The target accrual is 54 patients, to be achieved within 3.5 years.

¹ Patients with biopsy-proven TNBC requiring locoregional control or palliation with radiation to a measurable tumor.

² Obtain study staging only if unavailable 28 days prior to study registration. All patients will receive baseline PET-CT performed at MSKCC. An MR will be added if PET-CT is deemed to be insufficient for tumor evaluation by the study radiologist at baseline evaluation.

³ Radiation dose will be $250 \text{ cGy} \times 15 \text{ fx} = 3750 \text{ cGy}$ to the metastatic site delivered in 3 weeks for metastatic disease or $200 \text{ cGy} \times 25 \text{ fx} = 5000 \text{ cGy}$ delivered in 5 weeks to the chest wall, breast and/or regional lymph nodes, plus an optional 10-14 Gy boost to areas of gross tumor, for non-metastatic/locally recurrent disease.

⁴ The length of one Cisplatin cycle is 21 days. If cisplatin is withheld, the cycle count for treatment is also held.

⁵ Cisplatin will be once a week (± 3 days). The dose of cisplatin can be reduced in the event of toxicities defined in Section 4.2.1.

⁶ Following the completion of RT, pending no toxicities, but prior to the week 12 post RT evaluable timepoint, patients will continue to receive cisplatin or until POD, based on MD discretion.

⁷ At 12 ± 2 weeks after RT, all patients will receive PET-CT for treatment response and/or staging. MR will also be obtained if the patient had an MR at baseline.

⁸ PET-CT +/- MR will occur at 12 ± 2 weeks after RT. PET/CT +/- MRI q6 months after RT is recommended but not required.

2.0 OBJECTIVES AND SCIENTIFIC AIMS

The primary objective of this trial is to evaluate the performance of the MSK-HR repair assay as a biomarker in predicting response to concurrent cisplatin and RT in breast cancer patients with measurable metastatic or unresectable, locally advanced disease. Radiographic complete response (CR) of the irradiated tumor will be counted as a positive response to treatment. Radiographic response less than a CR, progression of the irradiated tumor or appearance of a new lesion within the irradiated field will be categorized as a failure to respond to treatment. All other sites of metastatic disease that is outside of the irradiated field will be monitored and counted toward disease progression.

Secondary objectives are to assess:

- Partial response, stable disease and progression of disease within the irradiated tumor as well as systemically (in sites distant to the irradiated tumor)
- Overall time to progression
- Toxicities of concurrent cisplatin and radiation

Exploratory objectives are to assess:

- Examine immune correlates to determine the impact of treatment on anti-tumor immunity and as a predictor of treatment response
- Determine the sensitivity of ctDNA detection in patients receiving chemoradiation for metastatic and locally recurrent TNBC
- Compare the efficacy of RECIST 1.1 vs. PET Response Criteria (PRC) as measurement tools for treatment response

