We anticipate that the most common discrepancy between PRC and RECIST 1.1 will be when there is a CR on PRC, but PR on RECIST 1.1. In these cases, PRC will be utilized for response

assessment. If PRC will be used, RECIST 1.1 is not required for the primary endpoint. However, for the secondary endpoints of comparing PRC to RECIST 1.1, RECIST 1.1 measurements will be done on the CT portion of the PET/CT.

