Exploratory objectives are to evaluate the association of tumor-infiltrating lymphocytes (TIL), other immune correlates within the tumor biopsy specimen and circulating tumor DNA as stated in section 3.6 and 5.4 as a predictor of treatment response. This will be done using a Wilcoxon rank-sum test. In a second exploratory objective, in patients who have both RECIST 1.1 and PRC assessments, agreement will be calculated and if there is a sufficient sample size, a McNemar's test will be done.

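### The planned agreement statistic and McNemar's test cannot show whether PRC or RECIST 1.1 is the better response measure; add an outcome table or limit the exploratory aim to agreement

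*Combined protocol and SAP*

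**What the plan says.** Section 2.0 lists among the exploratory objectives: "Compare the efficacy of RECIST 1.1 vs. PET Response Criteria (PRC) as measurement tools for treatment response". Section 1.0 puts the aim as "to compare the effectiveness of RECIST 1.1 criteria with PET Response Criteria in metabolically active tumors".

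The analysis is one sentence in Section 14.0. It is confined to the subset "in patients who have both RECIST 1.1 and PRC assessments", and there "agreement will be calculated and if there is a sufficient sample size, a McNemar's test will be done". The agreement statistic, the response categories to be compared and the number that counts as sufficient are not given.

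Section 12.0 makes PRC the generally preferred criterion and takes the paired RECIST 1.1 reading from the CT part of the PET/CT. It expects that "the most common discrepancy between PRC and RECIST 1.1 will be when there is a CR on PRC, but PR on RECIST 1.1", and settles such cases by rule: "In these cases, PRC will be utilized for response" assessment. Section 12.0 calls this comparison a secondary endpoint; Sections 1.0, 2.0 and 14.0 treat it as exploratory.

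**The concern.** Efficacy and effectiveness, applied to a measurement tool, ask which tool measures response better. Answering that needs something outside both tools: tissue, or what the tumor later does. The plan links neither to the two gradings.

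Section 12.0 already predicts the direction of disagreement, so a significant McNemar result would mostly confirm that PRC assigns CR more often than RECIST 1.1. That result looks the same whether the additional PRC CRs are controlled tumors or false CRs. Because PRC is also preferred for the primary CR endpoint, readers will want to know how tumors graded CR on PRC and PR on RECIST 1.1 fare later. The planned output does not tell them, and a small p-value could be taken as support for PRC.

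**Working it through.** **The plan's own figure.** There is none to reproduce: no sample size, power, alpha or expected discordance is stated for this comparison.

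**Inputs.** Section 14.0 gives the accrual target of 54 (the largest possible paired set if accrual meets it), assumed HRR deficiency of 40%, and assumed CR rates of 65% (HRR-deficient) and 30% (HRR-proficient). The discordant counts and the CR v non-CR split are assumptions made here.

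**Step 1: an illustrative table.** Overall CR = 0.4 × 0.65 + 0.6 × 0.30 = 0.44, and 0.44 × 54 = 23.8, so about 24 CRs by PRC. Suppose 8 of these are PR on RECIST 1.1 and none go the other way. The cells are: both CR 16, PRC-only CR 8, RECIST-only CR 0, neither 30.

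- Agreement = (16 + 30)/54 = 46/54 = 85.2%.
- Chance agreement = (24 × 16 + 30 × 38)/54² = 1524/2916 = 0.523.
- Kappa = (0.852 − 0.523)/(1 − 0.523) = 0.69.
- Exact two-sided McNemar p = 2 × 0.5⁸ = 0.0078.

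**Step 2: vary the truth and hold the table fixed.** Assume the concordant calls are correct.

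| Of the 8 discordant tumors, true CR | PRC correct | RECIST 1.1 correct | Agreement, kappa, p |
|---|---|---|---|
| 8 | 54/54 = 100% | 46/54 = 85.2% | 85.2%, 0.69, 0.0078 |
| 4 | 50/54 = 92.6% | 50/54 = 92.6% | 85.2%, 0.69, 0.0078 |
| 0 | 46/54 = 85.2% | 54/54 = 100% | 85.2%, 0.69, 0.0078 |

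The same planned output fits PRC being better, equal or worse.

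**Step 3: vary the discordance.** Exact two-sided p, with agreement out of 54:

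| PRC-only v RECIST-only CR | Agreement | p |
|---|---|---|
| 5 v 0 | 90.7% | 0.063 |
| 6 v 0 | 88.9% | 0.031 |
| 8 v 1 | 83.3% | 0.039 |
| 10 v 2 | 77.8% | 0.039 |

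Six discordant pairs, all in the direction that Section 12.0 expects, are enough for p < 0.05. The argument in Step 2 does not depend on the cell counts.

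**Step 4: is a reference outcome planned elsewhere?** Sections 5.3 and 10.0 schedule the study biopsy before treatment only. Section 14.0 compares time to progression by HRR status, not by PRC or RECIST category. Sections 9.0 and 10.0 make six-monthly imaging optional. No analysis ties either grading to a later outcome.

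**Step 5: can later progression serve?** Only with care. Section 12.0 carries the baseline criterion forward to follow-up, so in-field progression would mostly be graded by PRC, one of the two tools under comparison. It also records a cleared lesion as zero, which leaves a percentage rise from a PRC CR undefined. Section 4.2 determines study endpoints by 24 weeks after RT. With the response scan at 10 to 14 weeks, that leaves 24 − 14 = 10 to 24 − 10 = 14 weeks.

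**The case against.** The strongest defense is that the defect lies in the wording of the objective. Agreement between paired readings is a normal way to compare two response criteria, the aim is exploratory, McNemar's test is conditional on numbers, and Section 12.0 fixes in advance that PRC decides the expected discordance. Whatever this comparison shows, the primary CR calls do not change. Rewording the objective as agreement would remove the mismatch at no cost. All of this stands, and it makes the point minor. It does not make the planned analysis answer the question as now worded.

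The case against a large analytic repair is also sound. A reader might infer that McNemar's test should give way to a landmark comparison of c-indices for later in-field progression. The documents do not support that. The outcome would mostly be called by PRC, later imaging is optional, the endpoint window after the scan is short, and the comparison would rest on a few discordant patients. Cisplatin after the week-12 assessment is at the physician's discretion (Section 4.3.1), so the scan result may itself influence later treatment.

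The illustration is limited too. The 8 v 0 split is assumed, and 54 is a ceiling, because patients who progress or die before the scan may lack paired readings. It shows that the output carries no information on accuracy; it does not estimate an effect.

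**Conclusion.** The mismatch is real and minor. Even perfectly executed, the Section 14.0 analysis cannot rank the two criteria, because it uses no outcome outside them. In the illustration, agreement of 85%, kappa of 0.69 and p = 0.008 go with PRC accuracy anywhere from 85% to 100%, and RECIST 1.1 accuracy from 100% down to 85%. That rests on assumed cell counts, on concordant calls being correct and on a CR v non-CR split.

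Three stronger readings go too far. First, the two planned statistics do not both show which tool assigns CR more often: agreement shows only how often they match, and McNemar's test alone addresses the marginal difference. Second, the plan does not state that McNemar's test will use CR v non-CR; that is a reasonable inference from the primary endpoint. Third, the primary comparison by HRR status is not undermined: its criterion is set by rule in Section 12.0 and does not depend on this exploratory analysis.

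**What to change.** In Section 14.0:

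- Keep agreement, with a named statistic and a confidence interval, and McNemar's test on CR v non-CR. State that both are descriptive and do not rank the tools.
- Add a descriptive table running from the week-12 scan, in patients graded by both criteria and progression-free at that scan. Show later in-field progression in three groups: CR on PRC with PR on RECIST 1.1, concordant CR, and concordant non-CR. List any CR on RECIST 1.1 with non-CR on PRC as well. Give the number followed and the length of follow-up in each group.
- Define in-field progression for this table so that it does not rest on PRC or RECIST 1.1 alone, and so that it can be applied to a lesion recorded as zero.
- If such an outcome cannot be obtained, limit the objective in Sections 1.0 and 2.0, and any conclusion, to agreement between the criteria.
- Do not make a c-index difference the comparative analysis.

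The cost is a few sentences of wording and one table, using follow-up the trial already plans. The downside is imprecision: later imaging is optional, endpoint follow-up after the scan is short and discordant cases will be few. The table can inform how the discordant CRs are read, but it will not settle which tool is better.

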3.1 BACKGROUND AND RATIONALE

Triple negative breast cancer (TNBC), defined as estrogen receptor and progesterone receptor levels <1% and HER2-negative (0-1+ by immunohistochemistry or HER2/CEP17 ratio <2 or HER2 signals/cell <4 by in-situ hybridization [1]), comprises 12-17% of breast cancers. TNBC is associated with rapid growth, early metastasis and unfavorable prognosis compared to other subtypes of breast cancer [2]. Since targeted treatment options such as endocrine therapy and HER2-directed therapies are unavailable, chemotherapy is the mainstay of treatment. Although chemotherapy and radiation therapy (RT) are common treatments for palliation and local control in metastatic or recurrent breast cancer, there are no effective biomarkers that can reliably predict the sensitivity of these tumors to these treatments.

TNBCs are characterized by a genomic profile that is similar to those of breast cancer patients who are BRCA1-mutation carriers. This profile is indicative of defects in the BRCA pathway, therefore resulting in a “BRCA-like” phenotype. Although rarely mutated in sporadic breast cancer (<5% of breast cancer patients harbor germline mutations in either gene), BRCA1 expression has been reported to be reduced in a small number of sporadic tumors, particularly in TNBC [3-5]. BRCA1 and BRCA2 are only two of many proteins involved in executing HRR [6]. A subset of sporadic breast cancers may also have defects in HR, in the absence of mutations in either BRCA1 or BRCA2 [7-9].

3.2 Rationale for Homologous Recombination (HR) Repair Testing In the Clinic

BRCA1 and BRCA2 are essential for error-free repair of double strand breaks (DSB) induced by ionizing radiation and certain DNA damaging chemotherapeutic agents, through their activity in the BRCA1-BRCA2-RAD51 DNA repair pathway of homologous recombination (HR). In homologous recombination (HR), both BRCA1 and BRCA2 are required for the recruitment of Rad51 to sites of DSB's, with BRCA2 interacting directly with Rad51. Rad51 is a vital downstream protein required for homology search and strand invasion, using the sister chromatid as a template for error-free repair of the DSB. In the absence of HR, cells rely on more error-prone mechanisms, including non-homologous end-joining, in which pieces of DNA are pieced together in a quick but error-prone way, resulting in deletions of significant amounts of genetic material and chromosomal instability.

PARP is an important enzyme involved in base-excision repair which repairs endogenous or therapy-induced single strand breaks. Inhibition of that pathway by a PARP inhibitor results in the accumulation of large amounts of single strand breaks which can be converted to double strand

breaks at stalled replication forks. In HR-proficient cells, these DSB's are repaired by homology directed repair which is a Rad51-dependent process. In HR-deficient cells, however, such as cells with loss of BRCA1, BRCA2 or other proteins involved in the complex BRCA1-BRCA2 pathway, the repair machinery of the cell can be overwhelmed, leading to error-prone repair by alternative mechanisms such as non-homologous end joining, leading to chromosomal instability and cell death. Inhibition of homologous recombination or PARPs may be well tolerated in isolation, but combined inactivation of these distinct DNA-repair pathways, it can result in cell death through a process called "synthetic lethality."

In preclinical models, BRCA1 and BRCA2-deficient cells have been shown to be sensitive to PARP inhibitors. However, clinical studies utilizing PARP inhibitors in unselected sporadic TNBC have failed to show benefit of PARP inhibitors in improving progression-free survival [10]. These findings underscore the importance of assaying the function of the HRR pathway in order to better identify TNBC patients who would most likely to benefit from DNA repair-based therapies.

3.3 The Memorial Sloan Kettering HR Repair (HRR) Assay

There are two components of the MSK HRR assay. The first, the induction of RAD51 foci, is a functional assay that assesses HRR status in real-time, prior to the initiation of study treatment. The second, the CGH (comparative genomic hybridization) array, validates the RAD51 foci by detecting copy number changes in the genome that are characteristic of HRR status. Fresh tumor tissue is required for the RAD51 foci assay, whereas extracted DNA from the fresh tumor specimens is used for array-CGH studies. The assays will be conducted in the lab of [name].

The rationale for using both components of the assay is to detect HRR deficiency as determined by RAD51 foci assembly, and then to validate these results with the CGH read-out of the genomic architecture. We anticipate that validation with the array CGH will be particularly useful in identifying "conversion" patients in whom HRR-deficient status may have converted to HR-proficient status secondary to pre-treated with multiple systemic agents prior to study enrollment.

3.3.1 RAD51 Foci

DNA repair proteins accumulate into foci in the nuclei of cells following DNA damage including irradiation, and these foci can be detected by immunofluorescence and represent sites of ongoing repair. This method has proven to be a robust method of observing HR in cells [11]. Given its downstream location in the BRCA1-BRCA2 pathway of HR, the recruitment of Rad51 into foci correlates well with the ability to carry out HR and has been utilized to assay the integrity of the entire pathway. BRCA1 and BRCA2 deficient cells are unable to form RAD51 foci following exposure to ionizing radiation [12]. Powell et al. has previously reported the feasibility of quantifying ionizing radiation (IR) induced RAD51 and other DNA repair foci formation *ex vivo* in fresh pretreatment breast cancer specimens as a means of assessing the function of the BRCA1-BRCA2-RAD51 pathway[13].

[figure not shown]

Figure 2: Immunofluorescent representation of the induction of nuclear foci in human tumor cells with and without RT: a) There is prominent phosphorylation of histone H2AX (at serine 139) following 10Gy. H2AX was used as an upstream event in the DNA damage response as a control for cell viability and adequacy of the preparation. In one of the cells shown, there is recruitment of both BRCA1 and RAD51 into foci following 10Gy. At least 100 cells were counted in each condition (no RT vs RT) and cells were considered positive if they have ≥ 5 foci. The nuclei of the MCF 7 cells are stained blue with DAPI, and on the right following 10Gy, $>50\%$ increase in rad51 foci is visible after RT, suggesting an intact BRCA1-BRCA2 pathway b) The nuclei of the MCF 7 cells are stained blue with DAPI, and on the right following 10Gy. There was normal gammaH2AX foci formation upstream, but a failure to recruit BRCA1 or Rad51 into foci following 10Gy. This tumor was therefore deemed to have a defective BRCA1-BRCA2 pathway.

3.3.2 Array-CGH

Array CGH uses microarray technology to assess for copy number changes (genomic gains, heterozygous losses, high-level amplifications, homozygous deletions). DNA from a test sample and normal reference sample are labeled differentially using different fluorophores, and hybridized to several thousand probes. The probes are derived from most of the known genes and non-coding regions of the genome and printed on a glass slide.

The ratio of the fluorescence intensity of the test to that of the reference DNA is then calculated, to measure the copy number changes for a particular location in the genome. Typical CGH genomic profiles from breast cancers in BRCA1 and BRCA2 mutation carriers are characterized by prominent large segment deletions and some gains likely due to aberrant processing of chromatid breaks during mitosis. In contrast, sporadic tumors tend to have one of two types of genome profiles, with either very few larger altered segments or a high number of small copy number alterations throughout the genome, with occasional high-level amplification events.

[figure not shown]

Figure 3: Analysis of genomic profiles by array-CGH of 12 tumors grouped by HRR status: On the left are the 6 HRR-deficient tumors found to have functional defects in the BRCA1-BRCA2 pathway by the RAD51 foci assay. On the right are 6 HRR-proficient tumors. Gains are shown in red and losses are shown in blue. The 6 HRR-deficient tumors characteristically show a greater number of large deletions and some gains, compared to the 6 HRR-proficient tumors, displaying a BRCA-like genomic landscape with significantly more deletions of large segments of genetic material likely due to aberrant processing of chromatid breaks.

3.3.3 Exome Resequencing

To evaluate for homologous recombination pathway alterations in genes other than BRCA1 and BRCA2, we will obtain whole exome resequencing data through the MSK Genomics Core Facility using genomic DNA obtained from core biopsy samples and matched against normal tissue (buffy coat of peripheral blood samples). Exome resequencing of breast cancer samples in our pilot study that were MSK-HRR deficient and BRCA1/2 wild type revealed that 65% had potentially deleterious alterations in other components of the HR pathway (unpublished). Quality control of extracted DNA, and sequencing library preparation will be performed by the MSK Genomics Core Facility. We will use a data-analysis pipeline wherein germline variants will be filtered out of sequencing analyses using matched blood samples. Thus, germline alterations will not become apparent to researchers.

3.3.4 Preliminary Data on the Frequency of HRR Defects by Breast Cancer Subtype

The frequency of BRCA1-BRCA2-RAD51 pathway defects in sporadic breast cancer has been quantified using the MSK HRR assay in 60 invasive breast cancer patients receiving lumpectomy or mastectomy in whom fresh tumor tissue specimens were collected at the time of surgery (IRB protocol #10-093). Overall, seventeen of 60 (28%) tumors displayed defective RAD51 recruitment

following ex-vivo irradiation. HRR-deficiency was seen in all subtypes of breast cancer but was enriched in TNBC: 7 of 33 (21%) ER positive, 4 of 14(29%) HER2 amplified, and 6 of 13 (48%) TNBCs. HRR deficiency was not associated with low BRCA1 mRNA or protein expression. As noted above, HRR-deficient sporadic breast cancers displayed genomic landscapes characterized by large segment gains and losses due to genomic instability from loss of HR [14].

